8.7.4 Safety Laboratory Data

The laboratory tests listed in section 7.1.7 of the protocol will be listed and summarized. All laboratory tests including retests and reasons for retests will be included in the subject listings. In case of multiple measurements of a laboratory test at a given time point for a subject only these measurements will be retained for analysis:

1. Before the study vaccination, only the last measurement closest to the study vaccination.
2. After the study vaccination, only the first measurement closest on/or before the planned visit..

The reference ranges to categorize the results as “low” (values below the lower limit of the reference range), “normal” (values within the reference range) or “high” (values above the upper value of the reference range) will be those provided by the laboratory (as specified in the Clinical Specimen Lab Manual), which performed the tests. The corresponding grading scales can be found in Appendices C-E of the protocol.

8.7.5 Prior and Concomitant Medications

A **prior medication** is a medication used before the day of study vaccination (medication end date < study vaccination date).

A **post-vaccination medication** is a medication used only after study termination (i.e. medication start date > study termination date).

All other medications are **concomitant**.

When start and/or end dates of a medication intake are missing, the medication is considered as concomitant with the study vaccination schedule.

If the first study vaccination date is missing then the medication is considered as concomitant with the study vaccination schedule, provided that the study vaccine was administered to the subject.

8.8 Analysis Software

All data processing, summarization, and analyses will be performed using SAS[□]version 9.2 or higher (SAS Enterprise Guide 4.3).

8.9 Data Transformation

Distributions of antibodies are generally skewed to the right ([Nauta, 2010](#)). Therefore, prior to any statistical analysis that assumes normally distributed observations, antibody titers or concentrations will be \log_{10} -transformed. GMTs and their 95% CIs are computed by exponentiating (base 10) the least squares means and 95% CIs of the \log_{10} titers.

9. STUDY SUBJECTS**9.1 Disposition of Subjects and Withdrawals**

The following tables will be created:

- Number of randomized subjects.
- Number of subjects who received study medication.
- Number of randomized subjects who completed the study in each vaccine group.
- Number of subjects who discontinued after randomization, by dosage group and main reason.

The frequencies and percentages of subjects in each analysis set, study withdrawals, subgroups, and major protocol deviations will also be presented.

The time the subjects are under observation will be summarized by dosage group and overall using summary statistics (n, mean, SD, minimum, median, maximum). The number and percent of subjects at each visit will also be summarized.

10. DEMOGRAPHICS AND OTHER BASELINE CHARACTERISTICS

10.1 Demographics

Subjects will be summarized according to the subject's dosage group and overall.

Age, height, weight, and body mass index at enrollment will be summarized by reporting the mean, standard deviation, median, minimum and maximum, and will be calculated by dosage group and overall.

The frequencies and percentages of subjects by sex, race, and entry criteria met will be presented by dosage group and overall. Demographic data will be tabulated for the All Enrolled, All Exposed, Solicited Safety, Unsolicited Safety, Overall Safety, the FAS, and the PPS.

For females, the results of the pregnancy test at Screening and visit 1 will be listed.

10.2 Medical History

The frequencies and percentages of subjects in the All Enrolled Set with medical history will be presented by MedDRA system organ class and preferred term, by dosage group and overall for the All Enrolled Set. The same table will be created for the Overall Safety Set if such a set differs from the All Enrolled Set.

11. IMMUNOGENICITY ANALYSIS

11.1 Blood Samples

The frequencies and percentages of subjects in the All Enrolled Set with blood draws will be summarized overall and by vaccine group. A similar table will be created for the additional blood samples collected at Day 1, Day 4, Day 8, Day 29 and Day 181 in subjects who signed the separate Informed Consent form.

11.2 Primary Objectives Analysis

The primary immunogenicity endpoints are the GMTs measured by hSBA directed against MenC from samples collected on Day 1 (baseline, before vaccination) and Day 29 as well as the GMR of the titers (Day 29 / Day 1).

The primary immunogenicity analyses will be based on the PPS on Day 29. The primary endpoints will also be assessed using the FAS as a sensitivity analysis

Geometric Mean Titers

The logarithmically (base 10) transformed antibody titers will be modeled using an analysis of covariance (ANCOVA) model with a qualitative factor for the dosage of the LHD153R adjuvant (0, 12.5, 25, 50 or 100 µg) and log (base 10) pre-vaccination titer as a covariate. The adjusted GMT and the two-sided, 95% confidence intervals (CIs) of the GMT will be calculated based on this model as will the ratio of GMTs and corresponding CIs.

The adjusted GMT and two-sided 95% CIs will be constructed by exponentiation (base 10) of the least square means of the logarithmically transformed (base 10) antibody titer. The ratio of GMTs (LHD153R adjuvant dosage minus Men C control), and corresponding two-sided 95% CIs, will be constructed by exponentiation (base 10) of the least square differences obtained from this model. The model can be written as:

$$\log_{10} (y_{ik}) = \mu + \alpha_i + \beta x_{ik} + \varepsilon_{ik}$$

where μ represents a common overall mean, α_i represents the adjuvant dose group i effect, β represents the common slope for the \log_{10} pre-vaccination titer, x_{ik} for subject k in adjuvant dose group i , and ε_{ik} represents random error for subject k in adjuvant dose group i .

The following SAS[□] code will be used for this ANCOVA model:

```
ODS OUTPUT DIFFS=D_SET
      LSMEANS=L_SET;
PROC MIXED ORDER=data;
  CLASS adj_dosage;
  MODEL log_titer=adj_dosage log_pre/ddfM=KR;
  LSMEANS adj_dosage /DIFF CL;
RUN;
```

where:

ADJ_DOSAGE: adjuvant dosage (0, 12.5, 25, 50 or 100 µg),

D_SET= dataset containing the ratio of LS means of the \log_{10} -transformed titers (the ratio of GMTs and the two-sided 95% CIs will be constructed by exponentiation -base 10-, only the values where _adj_dosage=0 will be used),

LOG_PRE= \log_{10} -transformed value of pre-vaccination titer,

LOG_TITER=log10-transformed value of titer on Day 29,

L_SET=dataset containing the LS means of the log10-transformed titer for each adjuvant dosage (the adjusted GMT and two-sided 95% CIs will be constructed by exponentiation -base 10-).

Given that ALPHA=0.05 is the default value, there is no need to specify such a value in the LSMEANS statements to calculate the 95% CIs of the ratios of GMTs or the adjusted GMTs.

Geometric Mean Ratios

The logarithmically (base 10) transformed within subject ratio of antibody titers (Day 29/pre-vaccination) will be modeled using an analysis of variance (ANOVA) model with a qualitative factor for LHD153R adjuvant dosage (0, 12.5, 25, 50 or 100 μ g). The adjusted GMR and the two-sided, 95% CIs of the GMR will be calculated based on this model. The model can be written as:

$$\log_{10} (y_{ik}) = \mu + \alpha_i + \varepsilon_{ik}$$

where μ represents a common overall mean, α_i represents the adjuvant dose group i effect and ε_{ik} represents random error for subject k in adjuvant dose group i .

The following SAS[□]code will be used for this ANOVA model:

```
ODS OUTPUT LSMEANS=L_SET;
PROC MIXED;
  CLASS adj dosage;
  MODEL log_ws_ratio= adj dosage /ddfM=KR;
  LSMEANS adj dosage /DIFF CL;
RUN;
```

where:

ADJ_DOSAGE: adjuvant dosage (0, 12.5, 25, 50 or 100 μ g),

LOG_WS_RATIO=log10-transformed value of within subject ratio of antibody titers (Day 29/pre-vaccination),

L_SET=dataset containing the LS means of the log10-transformed ratio of antibody titers (the adjusted GMR and two-sided 95% CIs will be constructed for each adjuvant dosage by exponentiation -base 10-).

Given that ALPHA=0.05 is the default value in the LSMEANS statements, there is no need to specify such a value to calculate the 95% CIs of the adjusted GMRs.

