14. INTERIM ANALYSIS

14.1 Interim Analysis

A safety and immunogenicity interim analysis for the selection of an LHD153R adjuvant dosage will be performed based on the data collected through Day 29 from subjects enrolled in all cohorts. This analysis will be performed by personnel not involved in study decisions. The results will be unblinded at the group level thereby preserving the blind for individual subjects. No adjustment to the overall alpha will be performed as the data collected subsequent to this analysis involve secondary and exploratory endpoints.

The interim analysis is to be considered final with regards to the Immunogenicity and Safety Tables up to Day 29.

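### The Day 29 interim is meant to select an LHD153R dosage, but the hSBA and ELISA analyses report no dosage-versus-dosage ratio with a confidence interval

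*SAP*

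**What the plan says.** - **Purpose of the interim (SAP 14.1).** "A safety and immunogenicity interim analysis for the selection of an LHD153R adjuvant dosage will be performed based on the data collected through Day 29". All cohorts contribute. The section adds: "The interim analysis is to be considered final with regards to the Immunogenicity and Safety Tables up to Day 29".
- **Primary hSBA model (SAP 11.2, Geometric Mean Titers).** An ANCOVA on log10 titer has five dosage levels (0, 12.5, 25, 50 and 100 µg) and log10 baseline titer as covariate. The code line "LSMEANS adj_dosage /DIFF CL" requests differences with limits and names no control level. The notes under the code then restrict the differences dataset: "only the values where _adj_dosage=0 will be used". A second dataset holds the "LS means of the log10-transformed titer for each adjuvant dosage", from which adjusted GMTs with 95% CIs are reported.
- **GMR model (SAP 11.2, Geometric Mean Ratios).** Differences are again requested, but the only dataset saved is given by "ODS OUTPUT LSMEANS=L_SET".
- **Secondary endpoints (SAP 11.3).** The same models are applied to hSBA at the other days, and the same ANCOVA to ELISA. Percentages are given per dosage group with Clopper-Pearson intervals. No between-dosage difference is mentioned.
- **Addendum, sections 2.6 and 2.8.3.** For exploratory T-cell and innate-cell data, pairwise differences among the LHD153R groups are used to describe the effect of adjuvant dosage.

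**The concern.** The decision in section 14.1 lies between LHD153R dosages. The quantity that bears most directly on it is the ratio of one dosage's GMT to another's, with its interval. The plan computes these ratios for hSBA and then excludes them by an explicit rule, while the addendum keeps the analogous comparisons for exploratory cell data.

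The gap affects how a ranking is read. Four ratios to control share one control group, so overlap between two of their intervals says little about the precision of one dosage relative to another. Overlap of two per-dosage GMT intervals is a stricter yardstick than the direct interval. Whoever selects the dosage would see an ordering of four point estimates without the interval that belongs to the comparison.

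There is also a smaller coding point. The filter works on the underscore variable of the differences dataset, and the code sets `ORDER=data`. Which control contrasts the filter returns therefore depends on the order of dosage levels in the input data, which the SAP does not state.

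**Working it through.** **1. Counting contrasts.** Five levels give 5 × 4 / 2 = 10 pairs. Four involve the control, and 4 × 3 / 2 = 6 are between LHD153R dosages. The filter keeps 4 of 10 and none of the 6.

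**2. What can be recovered.** The point estimate of a dropped ratio is the quotient of two reported adjusted GMTs, or of two ratios to control. Its interval is not reported. For the GMR model, which has no covariate, a reader could rebuild it from two tabulated intervals. For the ANCOVA this is only approximate, because the groups share the baseline slope.

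**3. Width of the missing intervals.** SAP Table 1 gives 16 subjects in each LHD153R group and 4 × 4 = 16 pooled controls, 80 in all. The SAP text gives no SD of log10 hSBA titer and refers to the protocol and a sample size memo, so 0.6 is an assumption, with 0.4 to 0.8 as the range. With five group means and one slope, df = 80 − 6 = 74 and t(0.975, 74) = 1.993. Covariate imbalance is ignored.

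- Ratio of two GMTs: factor = 10^(1.993 × SD × √(2/16))
- Single GMT: factor = 10^(1.993 × SD / √16)

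| Assumed SD (log10) | Factor, ratio of two dosages | Factor, single GMT |
|---|---|---|
| 0.4 | 1.91 | 1.58 |
| 0.6 | 2.65 | 1.99 |
| 0.8 | 3.66 | 2.50 |

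Because the groups are of equal size, a dosage-versus-dosage ratio has about the same width as a dosage-versus-control ratio. With 12 evaluable subjects per group (df 54) the ratio factors rise to 2.13, 3.10 and 4.52.

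**4. Why comparing intervals by eye is a poor substitute (SD 0.6).**

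- The direct 95% CI for two dosages excludes 1 once their observed ratio exceeds 2.65.
- Two single-GMT intervals stop overlapping only at 1.99 × 1.99 = 3.96.
- Two ratio-to-control intervals stop overlapping only at 2.65 × 2.65, about 7.0.

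In the other direction, if all four dosages were equally immunogenic, simulation puts the gap between the highest and lowest observed GMT at about 2.0-fold on average (1.6 to 2.6 for SD 0.4 to 0.8). This is below 2.65, but it could pass for a dose effect in a table that shows only the ordering.

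**5. Sort order.** `PROC MIXED` pairs each level with every later level and puts the later one in the underscore variable. Rows passing the filter:

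| Order of levels in the data | Control contrasts returned |
|---|---|
| 12.5, 25, 50, 100, 0 | 4 |
| 12.5, 0, 25, 50, 100 | 1 (12.5 µg only) |
| 0, 12.5, 25, 50, 100 | 0 |

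In enrolment order, control subjects enter with the first block of Cohort 1 (SAP section 3), so at most the 12.5 µg row would survive.

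**The case against.** Much of the case for the plan as written stands.

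- **The control contrast follows the objectives.** SAP sections 2.1 and 2.2 compare the LHD153R vaccine with the control, and no primary or secondary immunogenicity objective compares dosages. A reader might infer that the primary analysis is wrong. It is not, and the control ratios should remain the primary contrasts.
- **The dosages are not left without comparison.** A reader might infer that nothing tabulated compares them. The SAP gives adjusted GMTs and GMRs with CIs, response percentages with CIs, and safety and laboratory summaries for every dosage group. These support a descriptive ranking and show how imprecise each group is.
- **Selection does not rest on hSBA alone.** Section 14.1 describes a combined safety and immunogenicity analysis. How the choice is made may be set out in the protocol, which is not at hand.
- **Sample size limits the trial more than the filter does.** A reader might infer that the filter is what stops the trial from separating dosages. The chance spread of the GMTs is the same with or without it. At 16 per group, power to separate two dosages that differ 2-fold is about 57%, 29% and 19% for SD 0.4, 0.6 and 0.8, and extra output does not change that.
- **The sort-order failure is conditional.** A reader might infer that the primary ratios will be lost. A dataset sorted with the control last gives all four, the text of 11.2 states the direction of the ratio, missing rows would be obvious, and section 16 requires independent validation.

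What remains is narrow. The interim has a stated between-dosage purpose, the direct ratios are computed and then excluded, and comparing other intervals by eye does not replace them.

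**Conclusion.** The point holds as a gap in reporting. No dosage-versus-dosage hSBA or ELISA ratio with a confidence interval is reported, although the Day 29 analysis is for dosage selection and its tables are final. Six of the ten computed hSBA contrasts are dropped, and the GMR model saves none. The primary control comparison is sound, and a descriptive ranking is possible.

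The missing intervals would be wide: a factor of about 2.65 either way at SD 0.6, and 1.9 to 3.7 for SD 0.4 to 0.8. These figures rest on the assumed SD and 16 evaluable subjects per group. This is a cheap improvement, not a fault that invalidates the analysis. The coding point is a precaution, since the SAP leaves the data order open.

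**What to change.** 1. In section 11.2, keep the four ratios to 0 µg as the primary contrasts. Also retain the six ratios between LHD153R dosages with unadjusted 95% CIs, labelled descriptive, as support for the dosage selection in 14.1. Apply the same to the ELISA GMCs in 11.3.
2. Save the differences dataset from the GMR model and report it in the same way.
3. Name 0 µg as the reference level in the code, so that the control contrasts and their direction do not depend on data order under `ORDER=data`.

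Cost: SAP wording, a small code change and additional table rows. No further subjects or models are needed, since the differences are already requested in the code. Leaving the intervals unadjusted agrees with section 8.4. The downside is six more imprecise intervals per endpoint that could be over-read as tests, hence the descriptive label.

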8.7.2 Immunogenicity

Values below the limit of quantification (recorded as “< LLQ”) will be set to half the lowest limit of quantification.

Titer greater or equal to a given threshold is defined as a binary variable for nonmissing values as:

= 1, if the titer is superior or equal to the given threshold (\geq 4-fold rise in hSBA titer),

= 0, otherwise.

Seroresponse is defined as a binary variable for subjects with non-missing values prevaccination and postvaccination as:

- For subjects with a prevaccination hSBA titer < 4:

= 1, if postvaccination titer \geq 8

- For subjects with a prevaccination hSBA titer ≥ 4 :

= 1, if post-vaccination titer increases at least 4 times the baseline hSBA titer

= 0, otherwise.

Geometric Mean Titer/Concentration

The GMT/GMC will be calculated using the following formula:

$$\text{GMT} = \sqrt[n]{t_1 t_2 \dots t_n} = \sqrt[n]{\log_{10}(t_1) + \log_{10}(t_2) + \dots + \log_{10}(t_n)} = 10^{\frac{1}{n} \sum_{i=1}^n \log_{10}(t_i)}$$

where t_1, t_2, \dots, t_n are n observed immunogenicity titers/concentrations.

Geometric Mean Ratio

Geometric mean ratios (GMRs) measure the changes in immunogenicity titers/concentrations *within* subjects.

The GMR will be calculated using the following formula:

$$\text{GMR} = \frac{\sqrt[n]{\log_{10}(v_{ij}) + \log_{10}(v_{ik})}}{\sqrt[n]{\log_{10}(v_{ij})}} = \frac{\sqrt[n]{\log_{10}(v_{ij}) + \log_{10}(v_{ik})}}{\sqrt[n]{\log_{10}(v_{ij})}} = 10^{\frac{1}{n} \sum_{k=1}^n \log_{10}(v_{ik}) - \frac{1}{n} \sum_{j=1}^n \log_{10}(v_{ij})}$$

where, for n subjects, v_{ij} and v_{ik} are observed immunogenicity titers/concentrations for subject i at time-points j and k , $j \neq k$.

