11.3 Secondary Objectives Analysis

The secondary immunogenicity endpoints are:

- GMTs and corresponding GMRs measured by hSBA directed against MenC for samples collected at Day 8 and Day181.
- Percentage of subjects with hSBA seroresponse at Days 8, 29, and 181. Seroresponse is defined as a post vaccination hSBA ≥ 8 for subjects with a baseline hSBA <4 or have an increase of at least 4 times the baseline hSBA level for subjects with prevaccination hSBA ≥ 4 .
- Antibody geometric mean concentrations (GMCs) against MenC measured by ELISA for samples collected on Days 1 (baseline, prior to vaccination), 8, 29, and 181.
- The percentage of subjects with at least a 4-fold increase in antibody concentrations to MenC as measured by ELISA on Day 8, 29, and 181 relative to baseline (Day 1).

These analyses will be based on the PPS.

In the case of the endpoint for the GMTs and corresponding GMRs measured by hSBA directed against MenC, the same statistical models (ANCOVA and ANOVA) as the one used for the primary objective will be applied.

In the case of the endpoint for the GMCs against MenC measured by ELISA, the same ANCOVA statistical model as the one used for the primary objective will be applied.

The percentage of subjects with seroresponse and associated Clopper-Pearson two-sided 95% as well as the percent of subjects with a >8 titer will be computed for each dosage group at Days 8, 29 and 181.

The percentage of subjects with a 4-fold increase in antibody concentrations to MenC from baseline as measured by ELISA and associated Clopper-Pearson two-sided 95% CIs will be computed for each dosage group at Days 8, 29 and 181.

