initial set of genes will be reduced by applying a non-specific filtering to the pooled samples coming from all available dosage groups, including the control group. Only those genes showing a between subject interquartile range, in the log2transformed fold change from baseline, ≥ 0.5 will be retained. Analysis Methods:

- a. To evaluate the LHD153R ability to upregulate the expression level of a given BTM at a specified time point the following hypothesis needs to be tested for each BTM:

$$H_0: (\mu_{LHD153-12.5} \leq \mu_{MenC}) \text{ and } (\mu_{LHD153-25} \leq \mu_{MenC}) \text{ and } (\mu_{LHD153-50} \leq \mu_{MenC}) \\ \text{and } (\mu_{LHD153-100} \leq \mu_{MenC})$$

$$H_\alpha: (\mu_{LHD153-12.5} > \mu_{MenC}) \text{ or } (\mu_{LHD153-25} > \mu_{MenC}) \text{ or } (\mu_{LHD153-50} > \mu_{MenC}) \\ \text{or } (\mu_{LHD153-100} > \mu_{MenC})$$

The module response, fold change from baseline at the 24 hour time point, will be analyzed using analysis of variance (ANOVA) with the module response as the dependent variable and a fixed effect for dosage group. The adjusted (model-based) geometric mean fold changes, adjusted ratios of geometric mean responses between vaccine dosage groups and the corresponding two-sided, 95%, confidence intervals will be calculated based on this model. Should the data violate the normality assumption, then a Kruskal-Wallis test will be performed instead, followed by pairwise testing of the dosage groups in the same manner as previously described.

All 10 BTMs will be evaluated and the p-values adjusted using the BenjaminiHochberg False Discovery Rate (FDR) control procedure. BTMs with an adjusted pvalue ≤ 0.05 will be examined further.

- b. The module-specific geometric mean fold changes will be summarized using unadjusted geometric means and corresponding two-sided, 95% CIs by vaccine dosage group for each blood sampling time point. Summary statistics will be completed by providing minimum, maximum, first and third quartiles as well as the median.

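### Does the 'adjusted' GMR in SAP section 11.2 need a baseline covariate that its ANOVA lacks?

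*SAP*

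**What the plan says.** Section 11.2 of the SAP gives two models for the primary hSBA endpoints.

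- **GMT at Day 29.** An ANCOVA of the log10 titer on dosage, with "log (base 10) pre-vaccination titer as a covariate". It yields an adjusted GMT per dosage and the ratio of each LHD153R dosage to the MenC control, with 95% CIs.
- **GMR, Day 29/Day 1.** The log10 within-subject ratio "will be modeled using an analysis of variance (ANOVA) model with a qualitative factor for LHD153R adjuvant dosage". Neither the equation nor the MODEL statement has another term. The text continues: "The adjusted GMR and the two-sided, 95% CIs of the GMR will be calculated based on this model". The word 'adjusted' is applied to the GMR three times in this subsection. The LSMEANS statement carries DIFF, but the code keeps only the group means: "ODS OUTPUT LSMEANS=L_SET".

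Section 8.7.2 defines the quantity: "Geometric mean ratios (GMRs) measure the changes in immunogenicity titers/concentrations" within subjects. Section 8.1 points to section 11.2 for all covariate adjustment. For hSBA at Days 8 and 181, section 11.3 says "the same statistical models (ANCOVA and ANOVA) as the one used for the primary objective will be applied". Section 14.1 states the use of the Day 29 results: "A safety and immunogenicity interim analysis for the selection of an LHD153R adjuvant dosage will be performed". Section 2.8.1 of Addendum No. 1 uses the same word for the same kind of one-way model and explains it: "The adjusted (model-based) geometric mean fold changes".

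**The concern.** Within one section, 'adjusted' means corrected for baseline when applied to the GMT and means nothing of the kind when applied to the GMR. A reader who has just seen the ANCOVA, and who knows from section 8.1 that section 11.2 holds the covariate adjustments, could take the five GMRs as comparable across dosages after allowing for baseline. They are not.

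Baseline differences are plausible here. The seroresponse definition splits subjects at a pre-vaccination titer of 4, so mixed baselines are expected. Each LHD153R group has 16 subjects. Groups B to E enter in successive cohorts, each randomized only against its own four controls. The Day 29 tables also inform the choice of adjuvant dosage. If someone ranked the dosages by GMR, part of the ranking could reflect where subjects started rather than what the adjuvant did.

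**Working it through.** The SAP states no SD, correlation, slope or power figure for the GMR, so there is no planned figure to reproduce. From the SAP come the group size (16 per LHD153R dosage; 4 × 4 = 16 pooled controls), the two models and the 95% level. Baseline SD, slope and correlation below are assumptions, shown as ranges.

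**1. What the ANOVA estimates.** With dosage as the only term, the LS mean is the raw group mean of the log10 ratio. In a simulated data set of 5 × 16 subjects, the control LS mean and the raw mean were both 1.0128. The interval uses the pooled residual variance, so it is model-based even though the point estimate is crude.

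**2. How a GMR comparison differs from the adjusted one.** Let dY and dX be the between-group differences in mean log10 Day 29 titer and mean log10 baseline titer, and β the within-group slope.

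- GMR contrast: dY − dX
- ANCOVA contrast: dY − β·dX
- Gap: (β − 1)·dX

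In the simulated data, fitted β = 0.290 and dX (12.5 µg minus control) = 0.4868 − 0.6766 = −0.1898. The gap is (0.290 − 1) × (−0.1898) = 0.1347, which matches 0.2423 (ANOVA) − 0.1076 (ANCOVA).

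**3. Size of the gap.** One standard error of dX is SD × √(2/16). The fold shift is 10 to the power |β − 1| × that value.

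| Assumed baseline SD (log10) | One SE of dX | β = 0.5 | β = 0.9 | β = 1 |
|---|---|---|---|---|
| 0.3 | 0.106 | 1.13 | 1.02 | 1.00 |
| 0.6 | 0.212 | 1.28 | 1.05 | 1.00 |
| 0.9 | 0.318 | 1.44 | 1.08 | 1.00 |

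In 20,000 simulated comparisons per slope, with both groups drawn from the same baseline distribution, the mean GMR contrast stayed within 0.0013 log10 of zero. The gap is a shift given the observed imbalance, not a bias over randomization.

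**4. Precision.** Assume equal Day 1 and Day 29 SDs with correlation r, so that the slope equals r.

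- SE ratio for a contrast, ANOVA to ANCOVA: √[2(1 − r)/(1 − r²)] = 1.414, 1.155, 1.069, 1.026 at r = 0, 0.5, 0.75, 0.9.
- SE ratio for a single group's GMR, which is what the code keeps: √{[2(1 − r)/16] / [(1 − r²)/16 + (1 − r)²/80]} = 1.291, 1.118, 1.054, 1.021.

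In a separate simulated case with slope 1, the ANOVA contrast interval was about 0.7% narrower (width ratio 0.993), because no slope has to be estimated.

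**5. What the covariate would add.** With log10 baseline in the GMR model, the slope becomes β − 1 and the residuals are those of the GMT ANCOVA. The LS mean at the overall mean baseline x̄ is

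μ + αᵢ + (β − 1)x̄ = [μ + αᵢ + βx̄] − x̄.

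Each GMR is then the adjusted GMT divided by one constant, 10^x̄. In the simulated data the four contrasts against control were identical in both ANCOVAs: 0.1076, 0.0848, −0.0265 and −0.0194. The amended GMR would repeat the planned GMT analysis on a shifted scale.

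**The case for a change.** The best argument for a change is that the GMR is a primary endpoint under a comparative objective, the label suggests an adjustment that is absent, and the SAP never says that comparisons between dosages rest on the GMT ratio. The staggered cohorts strengthen it: differences in baseline between dosages need not be chance alone, so unbiasedness over randomization is limited comfort. DIFF in the GMR code also leaves a crude contrast one step from being printed. The remedy would cost one label and one sentence.

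The description stands. The label is loose, and a clearer word would read better. But the harm needs a comparison that the plan does not make. Section 11.2 asks for one GMR and interval per dosage, and the saved output matches that request, so the unused DIFF option is idle. The only between-dosage ratio specified is the baseline-adjusted one, so a statement that comparisons rest on it would record what the plan already does. No dosage selection rule refers to the GMR. The addendum is a later document and does not define the term for section 11.2, but it shows 'adjusted' being used to mean 'model-based'.

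**Conclusion.** The observation is accurate but calls for no change. The GMR in section 11.2 is the crude geometric mean fold rise with a pooled-variance interval, and it validly estimates the within-subject change defined in section 8.7.2. The baseline-adjusted comparison of dosages is already planned through the ANCOVA GMT ratio at Day 29, and again at Days 8 and 181. Reporting an adjusted titer ratio beside a crude fold rise is coherent, and putting the covariate in both models would remove the crude fold rise without adding information.

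The sizes above (1.13- to 1.44-fold at slope 0.5, 1.02- to 1.08-fold at slope 0.9, none at slope 1) apply only to an informal side-by-side reading of GMRs. They rest on assumed SDs and slopes that the SAP does not give. The wording is a clerical looseness that the printed equation and code resolve.
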